The gold standard for a diagnosis of EILO is a continuous laryngoscopy exercise (CLE) test, in which a flexible endoscope is used to monitor the laryngeal movement in real-time during exercise (Hall, et al., 2016). The tip of the endoscope is positioned in the mesopharynx (identified in Figure 1) by the clinician, who uses the live image from the endoscope to guide its position. A securing headgear is essential to keep the endoscope in a fixed position while the patient exercises, both to achieve a stable image and for the safety of the patient. An example of a CLE test set-up is displayed in Figure 2. This method of investigation is not currently offered by LUHFT, and other centres we have contacted provide the service using a non-CE/UKCA marked headgear.

[figure not shown]

Figure 1: showing the location of the mesopharynx, taken from (James F. Bosma M.D., 1986)

[figure not shown]

Figure 2: Continuous laryngoscopy exercise (CLE) test (Hall, et al., 2016)

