6.2 Primary and Secondary Endpoints/Outcome Measures

6.2.1 Primary Outcome Measure

Device effectiveness, measured by the proportion of CLE tests where the endoscopy image was clear and stable enough to allow a diagnosis of EILO to be confirmed or ruled out.

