6.4.4 Subsequent assessments

Following the consultation appointment, the participant will attend one investigation appointment to undergo the CLE test on-site at the Outpatient Department, Alexandra Wing, Broadgreen Hospital. There will be no follow-up assessments.

On the day of the investigation appointment, the Principal Investigator will address any questions or concerns before the investigation begins. If the participant still wishes to partake in the study, signed consent will be obtained from the participant. The right of the participant to refuse to participate without giving reasons will be respected. After the participant has entered the study the clinician remains free to give alternative treatment to that specified in the protocol at any stage if he/she feels it is in the participant's best interest, but the reasons

for doing so should be recorded. In these cases, the participants remain within the study for the purposes of data analysis.

Eligibility will be reviewed for any changes, ensuring that the participant meets the inclusion criteria and none of the exclusion criteria apply. As part of this, the circumference of the participant's head around the forehead will be measured and recorded. Signed consent will then be obtained. The participant will then undergo the CLE test following standard clinical practice.

The order of events of the aspects of the investigation related to the headgear will be:

1. The headgear is prepared for use.
2. The headgear is fitted onto the participant's head.
3. The endoscope is inserted into the participant.
4. The endoscope is fitted onto the headgear.
5. The CLE test is carried out.
6. The endoscope is removed from the headgear.
7. The endoscope is removed from the participant.
8. The headgear is removed from the participant.
9. The headgear is cleaned and stored.

Following completion of the CLE test, the participant will complete a questionnaire:

- How tolerable was the headgear during the investigation?
 - 1) Highly intolerable
 - 2) Intolerable
 - 3) Tolerable
 - 4) Highly tolerable
- Please tell us any concerns about the headgear, thinking about how comfortable it was, how hot your head felt, the weight of the headgear, how secure it felt and the impact of the headgear on your performance during the investigation.

Following the appointment, the clinician will complete a questionnaire including:

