- Was the endoscopy image clear and stable enough to allow a diagnosis of EILO to be confirmed or ruled out? (Note that participants are withdrawn from the study if the

CLE test is unable to allow a diagnosis of EILO to be confirmed or ruled out due to reasons unrelated to the headgear.)

- How easy was it to use the headgear?

- 1) Very hard to use;
- 2) Hard to use;
- 3) Neither hard nor easy to use;
- 4) Easy to use;
- 5) Very easy to use.

- Please record any concerns about the headgear, thinking particularly about set-up, operation and cleaning.

Data will be handled as detailed in Section 13 Data Handling and Record Keeping.

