9. STATISTICS

9.1 Description of Statistical Methods

A single proportion test will be applied to the primary outcome measure (see Section 6.2.1), using a reference proportion of 49 in 50. This is derived from a clinical estimate of the threshold for acceptable performance of the headgear being where the resulting endoscopy image is not sufficiently clear and stable in no more than 1 in 50 cases.

The secondary outcome measures (see Section 6.2.2) will be used as follows:

- The device usability and tolerability ratings will be used to support the risk/benefit ratio assessment of the device.
- Device usability and tolerability subjective feedback will be used to inform and prioritise how residual risks associated with usability and tolerability can be reduced.

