9.2 The Number of Participants

The number of participants is limited to 30 for practical reasons, based on the expected rate that participants can be recruited.

The following rationale was applied to determine this as an acceptable number of samples:

⁴ <https://www.hra.nhs.uk/approvals-amendments/managing-your-approval/safety-reporting/>, accessed 16/Aug/2021

- This is a Class I (MDD), low-risk device, and risk management according to ISO 14971 has been used to predict a favourable overall risk/benefit ratio.
- Bench testing has been carried out to verify that the design meets the specifications.
- Limited validation of the headgear has been carried out to partially show that the device is fit for purpose. This included testing on humans but without the endoscope inserted into them. The results demonstrated to a large extent that the design is safe and effective.

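### The primary outcome does not ask whether HALOS held the endoscope, so a diagnostic test completed after the headgear failed can count as a device success, or be withdrawn and replaced

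*Combined protocol and SAP*

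**What the plan says.** Section 4.2 gives the purpose of the device: "A securing headgear is essential to keep the endoscope in a fixed position while the patient exercises".

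Section 6.2.1 and the synopsis define device effectiveness as "measured by the proportion of CLE tests where the endoscopy image was clear and stable enough to allow a diagnosis of EILO to be confirmed" (the sentence goes on to include ruling it out). The matching item on the clinician questionnaire in 6.4.4 is: "Was the endoscopy image clear and stable enough to allow a diagnosis of EILO to be confirmed or ruled out". Neither asks how the endoscope was held.

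Section 6.4.4 also says that, once a participant has entered, "the clinician remains free to give alternative treatment to that specified in the protocol at any stage" if this serves the participant's interest. The reasons are to be recorded. It then says: "In these cases, the participants remain within the study for the purposes of data analysis".

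Section 6.5 allows the investigator to discontinue a participant for, among other reasons, a significant protocol deviation, and says that withdrawn participants are replaced. Section 9.7 includes all eligible participants in the analysis. Section 9.1 tests the primary proportion against 49 in 50, and section 9.3 sets the significance level at 0.01. Nothing in section 9 says how a test with a departure is scored.

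**The concern.** The outcome is labelled device effectiveness but measures image adequacy. The two agree as long as HALOS is what keeps the endoscope in place. They separate when HALOS loses its hold during exercise, the endoscope is supported by other means, and the image is still diagnostic. The device has then failed at its one function, yet the truthful answer to the questionnaire item is yes.

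The protocol offers two treatments of that case, and neither counts it as a failure. Under 6.4.4 the participant stays in the analysis and the image question decides the score. Under 6.5 the participant may be removed and another recruited. The existing carve-out, in the questionnaire note and the last withdrawal reason in 6.5, does not help. It covers tests that were not diagnostic for reasons unrelated to the headgear, which is the opposite situation.

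At stake is the primary objective, whether HALOS is suitable for CLE tests. The error can only favour the device.

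**Working it through.** **Inputs.** n = 30 (9.2: "The number of participants is limited to 30 for practical reasons, based on the expected rate that participants can be recruited"). Reference proportion 0.98 (9.1: "using a reference proportion of 49 in 50"). Significance level 0.01 (9.3). Section 9.1 says only that "A single proportion test will be applied to the primary outcome measure"; whether it is exact or approximate, and its direction, are not stated. The sample size was not derived from power, so there is no planned power figure to reproduce. The number of tests completed without HALOS holding the endoscope is not given and is treated below as an assumption.

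**Step 1: weight of one test.** 1/30 = 3.3 percentage points, against a tolerated failure rate of 1/50 = 2%.

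**Step 2: the plan's test.** With F failures, F ~ Binomial(30, 0.02) at the reference. The exact p-value for performance below the reference is P(F ≥ f). One- and two-sided exact p-values agree for these outcomes.

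| Failures | Successes | Proportion | Exact p |
|---|---|---|---|
| 1 | 29/30 | 96.7% | 0.455 |
| 2 | 28/30 | 93.3% | 0.121 |
| 3 | 27/30 | 90.0% | 0.022 |
| 4 | 26/30 | 86.7% | 0.0029 |

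The exact test at 0.01 first rejects at 4 failures. If one of those 4 is scored as a success, the result is 27/30 and no longer significant. A one-sided normal approximation first rejects at 3 failures (z = (0.900 − 0.98)/√(0.98 × 0.02/30) = −3.13, p = 0.0009) and not at 2 (p = 0.034). The boundary moves, but one test still decides the result there.

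In the other direction, 30/30 gives p = 0.98^30 = 0.545. At this sample size the test can therefore only ever find the device below the reference, so its ability to do that is what the scoring gap weakens.

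**Step 3: illustration of both routes.** Let s be the true proportion of tests with a diagnostic image while HALOS holds the endoscope, and r the share of the remaining tests completed with a diagnostic image by other means. Both are assumed.

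- Scored as success: s + (1 − s)r.
- Withdrawn and replaced: s / [s + (1 − s)(1 − r)].

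| Assumed s, r | Proportion: true / scored as success / replaced | P(4 or more failures): true / scored as success / replaced |
|---|---|---|
| 0.90, 0.5 | 0.90 / 0.95 / 0.947 | 35.3% / 6.1% / 7.1% |
| 0.80, 0.5 | 0.80 / 0.90 / 0.889 | 87.7% / 35.3% / 43.1% |
| any s, r = 0 | no change | no change |

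Both routes raise the proportion and lower the chance of detecting a device that falls short. With no such tests there is no bias.

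**The case against.** The strongest case against runs as follows.

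- **The scoring is undefined.** A reader might infer that the protocol counts these tests as successes. It does not say so. A literal reading of the image question permits that score, and a clinician who lost the image when the clamp slipped could answer no. This stands: the defect is a missing rule.
- **The scenario is not in the documents.** The departure clause is a general statement about freedom of care and does not mention supporting the endoscope by hand. A reader might also think of a substitute fixing device. Section 4.4 says there is no commercial option and that CLE tests are not possible at this Trust without a specialised headgear, and section 7.1 describes only two HALOS units, so that example fits poorly. The gap remains, because the outcome definition is silent on how the endoscope was held whatever that clause covers.
- **Re-seating is different.** An endoscope put back in the clamp is again held by HALOS. Treating every re-seating as a failure would be a stricter endpoint, and the 1-in-50 limit in 9.1 was set for image adequacy. This stands.
- **One test need not matter.** A reader might infer that a single such test changes the conclusion, because 30/30 lies above 98% and 29/30 below it. That compares raw proportions. Under the exact test neither 29/30 (p = 0.455) nor 28/30 (p = 0.121) is significant.
- **Failures would be seen elsewhere.** Reasons for departures, the usability rating, free-text concerns and device deficiency reports may all reveal them. They may, but none of these enters the primary proportion.

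**Conclusion.** The concern holds as a gap in the endpoint definition. A diagnostic test completed without HALOS holding the endoscope, because HALOS failed to hold it, can be scored as a device success under 6.4.4 or withdrawn and replaced under 6.5. Measured against the proportion of tests in which HALOS did its job, both routes bias effectiveness upward.

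The size cannot be computed, because the documents give no expected number of such tests, and it could be zero. What can be said is that each one is worth 3.3 points and that the test result changes only at its boundary (3 against 4 failures for the exact test). The detection probabilities above rest on assumed values of s and r and show direction and scale only.

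The documents do not support saying that these tests are scored as successes by rule, that re-seating is a device failure, or that one case decides the study. The point still merits a change: the correction is small, the bias has one direction, and support that was not recorded at the time may not be recoverable afterwards.

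**What to change.** 1. In the synopsis and 6.2.1, define success as a diagnostic image obtained with the endoscope held by HALOS.
2. Add one item to the clinician questionnaire in 6.4.4: after exercise began, was the endoscope supported other than by HALOS, or re-seated, and was this because of the headgear?
3. State in section 9 that a test completed without HALOS holding the endoscope for a headgear-related reason is a failure on the primary outcome.
4. Record re-seating in HALOS separately and handle it in a sensitivity analysis, because the 1-in-50 limit was set for image adequacy.
5. Report the image-only proportion alongside.
6. Reconcile 6.4.4 (participants stay in the analysis after a departure) with 6.5 (withdrawal and replacement for a protocol deviation), so that headgear-related failures stay in the denominator.

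The cost is one questionnaire item, a few sentences of protocol text and a possibly less favourable proportion. These changes concern recording and scoring only; the clinician's freedom to act is untouched.

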6.3.3 Exclusion Criteria

The participant may not enter the study if ANY of the following apply:

- Pain, sore areas, broken skin at the site of contact with the headgear.
- Devices, e.g. cochlear implants, that impede the use of the headgear.
- Head circumference is less than 50cm or greater than 63cm, reflecting the 3rd centile for females and 97th centile for males, respectively (Bushby, 1992).
- Exclusion criteria for endoscopy procedures:
 - Skull base/facial surgery or fracture within the previous six weeks
 - Major or life threatening epistaxis within the previous six weeks
 - Trauma to nasal cavity secondary to surgery or injury within the previous six weeks
 - Sino-nasal and anterior skull base tumours/surgery
 - Nasopharyngeal stenosis
 - Craniofacial anomalies
 - Hereditary haemorrhagic telangiectasia
 - Severe movement disorders and/or severe agitation
 - Vasovagal history
 - Bleeding risks
- Any other exclusion criteria as identified by the current endoscopy procedure.

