6.5 Discontinuation/ Withdrawal of Participants from Study Treatment

Each participant has the right to withdraw study at any time. In addition, the investigator may discontinue a participant from the study at any time if the investigator considers it necessary for any reason including:

- Pregnancy
- Ineligibility (either arising during the study or retrospective having been overlooked at screening)
- Significant protocol deviation
- Significant non-compliance with study requirements
- An adverse event, adverse device effect, serious adverse device effect or unanticipated adverse device effect which results in cessation of the CLE test or inability to continue to comply with study procedures
- Consent withdrawn
- If the participant cannot wear the headgear, e.g. it does not fit.
- If the CLE test is unable to allow a diagnosis of EILO to be confirmed or ruled out due to reasons unrelated to the headgear, e.g. the participant cannot tolerate the endoscopy.

Withdrawn participants will be replaced.

The reason for withdrawal will be recorded in the Case Report Form (CRF).

If the participant is withdrawn due to an adverse event, the investigator will arrange for follow-up visits or telephone calls until the adverse event has resolved or stabilised.

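### Minor: no rule secures a tolerability form when the headgear stops a test early, so the tolerability fraction may err in the device's favour

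*Combined protocol and SAP*

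**What the plan says.** Section 6.2.2 takes two secondary outcomes from one participant form. Item iii is the share of ratings of 3 or 4 on a four-point tolerability scale. Item iv is free-text comment on comfort, including heat, weight, security and effect on performance. Section 6.4.4 states one moment for this form: "Following completion of the CLE test, the participant will complete a questionnaire". The clinician's form, in the same section, is due after the appointment and does not depend on whether the test was completed.

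Section 6.5 gives the investigator discretion to withdraw a participant. Two of the listed grounds can arise from the headgear: "If the participant cannot wear the headgear, e.g. it does not fit", and an adverse event or device effect "which results in cessation of the CLE test or inability to continue to comply with study procedures". The section continues: "Withdrawn participants will be replaced". At withdrawal it asks for the reason in the CRF and, where an adverse event was the cause, follow-up of that event. It mentions neither a rating nor comments.

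A further ground is a test that gives no diagnosis "due to reasons unrelated to the headgear, e.g. the participant cannot tolerate the endoscopy". The note in the clinician's form (section 6.4.4) carries the same limit.

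Under section 9.1 the ratings support the risk/benefit assessment and the feedback steers reduction of residual risk, with no test or threshold. Section 9.7 says only that eligible participants are analysed. Section 9.5 ignores data missing completely at random up to 5%, and imputes data missing at random by a method it does not name.

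**The concern.** The people most likely to find the headgear hard to tolerate include those whose test it cuts short. If their only stated chance to fill in the form comes after a completed test, and they are then replaced by someone who does complete, the fraction describes completers. It would be too favourable if those left out would have rated lower. Their prompted comments, which section 6.2.2 treats as an outcome in its own right, would also go uncollected.

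The analysis cannot repair this later. There is one test appointment and no scheduled follow-up assessment, so a form not given that day has no later collection point in the protocol.

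**Working it through.** The plan has no figure to reproduce: tolerability has no target, significance level or power, and the 30 participants are a practical limit (section 9.2). The check is therefore a reading of the rules case by case, followed by an illustration.

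**Which participants can go unrated**

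| Case | Sections 6.5, 9.4 and 15 | Participant form |
|---|---|---|
| Test completed, diagnosis possible | No withdrawal | Given |
| Test completed, no diagnosis because of the headgear | Not in itself a listed ground: the ground is limited to causes unrelated to the headgear | Given |
| Headgear cannot be worn | May be withdrawn and replaced | Not stated; little or no wear to rate |
| Test stopped by a non-serious device effect | May be withdrawn and replaced | Not stated |
| Test stopped by a serious device effect | Trial ends | Not stated, but the event is reported under section 8.3 |

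The fourth row is the core of the gap.

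**Whether another section closes it**

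- Section 9.7 may be read as keeping eligible withdrawn participants in the analysis. It cannot supply a rating that was never collected.
- Section 6.4.4 keeps participants in the analysis when alternative treatment is given. It has no matching sentence for withdrawal.
- Section 9.5 covers data missing completely at random or at random. A rating missing because of the headgear may be neither.

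**Illustration**

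Assumptions, none from the documents: 27 of the 30 completers rate 3 or 4, and k headgear-related withdrawals are unrated and replaced.

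- Reported fraction: 27/30 = 90.0%, exact (Clopper-Pearson) 95% interval 73.5% to 97.9%.
- All k counted as unfavourable, 27/(30 + k): k = 1 gives 27/31 = 87.1%; k = 3 gives 27/33 = 81.8%.
- All k counted as favourable, (27 + k)/(30 + k): k = 1 gives 28/31 = 90.3%; k = 3 gives 30/33 = 90.9%.
- Imputed at the completer rate, (27 + 0.9k)/(30 + k): k = 1 gives 27.9/31 = 90.0%; k = 3 gives 29.7/33 = 90.0%. Such imputation returns the completers' fraction.
- If all 30 completers rate favourably, 30/30 = 100% becomes 30/31 = 96.8% (k = 1) or 30/33 = 90.9% (k = 3) with all k unfavourable.

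For 27/30, every shifted value lies inside the interval.

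**The case against.** The strongest reply is that section 6.4.4 states timing, not a condition. Section 6.2.2 calls the form a post-test questionnaire, a stopped test is also followed by a post-test moment, and the participant is still in the room. Section 6.5 does not say that data collection ends at withdrawal. The CRF, which section 6.6 makes the source document for both questionnaires, may also say when the form is given. This is a fair reading, and it means that the protocol excludes nobody by rule. What stands is that no protocol sentence covers the stopped test, so collection depends on how each session is handled.

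The affected group is also narrow. Head-size limits ("Head circumference is less than 50cm or greater than 63cm") and the other exclusions reduce failures to fit. The form asks about tolerability during the investigation, so someone the headgear never fitted has little to rate. Withdrawal is discretionary, and serious device effects end the trial. Bias needs a non-serious stop, a decision to withdraw, no form, and a less favourable rating. This limits the severity but does not supply the missing rule.

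Three stronger readings are tempting but not supported:

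- **That hazard information is lost.** The clinician's form follows the appointment and asks for concerns about the headgear. Section 6.2.2 provides for observation throughout the session. Adverse events (section 8.2), device deficiencies that could have led to a serious device effect (section 8.3) and withdrawal reasons (section 6.5) are all captured. Only the participant's own rating and prompted comments are exposed.
- **That tests made non-diagnostic by the headgear are withdrawn.** The listed ground applies where the "CLE test is unable to allow a diagnosis of EILO to be confirmed or ruled out due to reasons unrelated to the headgear", so a headgear cause is not in itself a listed reason. The list is not exhaustive, but it points the other way.
- **That the fraction is overstated by a known amount.** The documents give no withdrawal rate, and treating every failure to fit as intolerable would inflate any figure.

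**Conclusion.** The point holds as a minor one. The protocol does not secure a tolerability rating or comments from a participant whose test stops early for a non-serious headgear-related reason and who is then replaced. If this happens, and those participants would have rated less favourably than completers, the fraction errs in the device's favour.

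The amount is unknown. On the assumed 27/30, one such participant counted as unfavourable moves the result by 90.0 − 87.1 = 2.9 percentage points, and three move it by 90.0 − 81.8 = 8.2 points. Both shifts are smaller than the sampling uncertainty. If those participants would have rated favourably, the fraction is slightly understated instead. No stated decision turns on it, because the endpoint is secondary and has no threshold. The reason to act is that an uncollected form cannot be recovered and collecting it is cheap.

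**What to change.** - **Section 6.4.4:** give the participant form at the end of the session to everyone on whom the headgear was fitted, whether or not the test was completed, unless they have withdrawn consent to data collection. Leave the clinician form's timing as it is: it already does not depend on completion, and it asks about cleaning, which comes after the headgear is removed.
- **Sections 6.5 and 9.7:** state that ratings and comments collected from participants withdrawn for headgear-related reasons stay in the analysis even if those participants are replaced. Report the numbers of failures to fit and of headgear-related stops beside the fraction. Do not score failures to fit as tolerability failures.
- **Section 9.5:** state that a rating missing for a headgear-related reason is not imputed from completers' ratings.
- **Optional:** one sensitivity line counting unrated headgear-related stops as below the cut-off.

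The cost is a few sentences, written before data collection. The form exists and the participant is present. Sample size and the primary test are unchanged. The downside is that the reported fraction may be slightly lower.

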6.2.2 Secondary Outcome Measures

- i) **Device usability rating**, measured by the fraction of subjective usability ratings ≥ 4 on the post-test questionnaire. Clinician-reported usability will be scored on a five-point LIKERT scale² ranging from 1 (very hard to use) to 5 (very easy to use). Observations will be made throughout the session.
- ii) **Device usability subjective feedback**, focussing on any clinician-reported concerns regarding set-up, operation and cleaning.
- iii) **Device tolerability ratings**, measured by the fraction of subjective tolerability ratings ≥ 3 on the post-test questionnaire. Participant-reported tolerability will be scored on a four-point LIKERT scale ranging from 1 (very intolerable) to 4 (very tolerable).
- iv) **Device tolerability subjective feedback**, focussing on any participant-reported concerns regarding the comfort of the headgear including how hot their head felt, weight of the headgear, how secure the headgear felt and the impact of the headgear on their performance during the investigation.

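### The post-test forms collect the named comfort and usability aspects only as free text, so section 9.1 would set risk priorities without a per-aspect frequency or severity

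*Combined protocol and SAP*

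**What the plan says.** Section 6.2.2 lists four secondary outcomes. Outcomes i and iii are ratings reduced to a fraction; tolerability, for example, is "measured by the fraction of subjective tolerability ratings ≥ 3 on the post-test questionnaire". Outcomes ii and iv are subjective feedback on named aspects: three for the clinician and five for the participant.

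Section 6.4.4 describes the two forms.

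- **Participant.** There is one four-point item, "How tolerable was the headgear during the investigation", and one comment prompt: "Please tell us any concerns about the headgear, thinking about how comfortable it was, how hot your head felt", continuing with its weight and then "how secure it felt and the impact of the headgear on your performance during the investigation".
- **Clinician.** The form is introduced by "Following the appointment, the clinician will complete a questionnaire including". The items then listed are a yes/no question on image adequacy (the primary endpoint), one five-point ease-of-use rating, and one comment prompt: "Please record any concerns about the headgear, thinking particularly about set-up, operation and cleaning".

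Section 9.1 assigns the ratings to the risk/benefit assessment. The comments are to be "used to inform and prioritise how residual risks associated with usability and tolerability can be reduced". No method of coding or ranking comments is given. Section 5.2 sets as secondary objectives the validation of existing risk scores and of hazard mitigations, and the discovery of unforeseen hazards, usability ones in particular. Section 9.5 has a general missing-data rule that does not mention comments.

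**The concern.** The outcomes are defined by aspect, but the forms do not measure by aspect. A problem with heat or cleaning reaches the data only if someone writes it down. If nothing is written, the form does not show whether there was no problem, the problem was too minor to mention, or the box was skipped. The overall rating cannot settle this, because it is not tied to any aspect.

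Two secondary uses of the data are at stake. To prioritise risk reduction, or to check a risk score, it helps to know how often each problem occurred and how bad it was. As the forms are described, neither would be known for any aspect. Each participant has one test appointment and no follow-up (section 6.1), so what the form misses is not picked up later. Section 9.2 says that earlier human testing was done without the endoscope inserted, so these forms are the plan's first planned ratings of the headgear with an endoscope in place.

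**Working it through.** The plan states no figure on this point. The sample size of 30 is a practical limit (section 9.2), so there is nothing to reproduce. The check is a comparison of items, followed by illustrations.

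**1. Items against outcomes**

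| Form | Aspects named in 6.2.2 | Aspects with their own item in 6.4.4 | Comment prompts |
|---|---|---|---|
| Participant | 5 | 0 | 1 |
| Clinician | 3 | 0 | 1 |

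**2. What a blank does to one aspect's rate.** The counts are assumed: x = 3 participants of n = 30 mention the aspect, and b leave the box empty.

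- Blank means no problem: x/n.
- Blank means missing: x/(n − b).
- Every blank hides the problem: (x + b)/n.

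| b | x/n | x/(n − b) | (x + b)/n |
|---|---|---|---|
| 5 | 3/30 = 10% | 3/25 = 12% | 8/30 = 27% |
| 10 | 3/30 = 10% | 3/20 = 15% | 13/30 = 43% |
| 20 | 3/30 = 10% | 3/10 = 30% | 23/30 = 77% |

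The last column still assumes that people who commented on something else did not have this problem. Without that assumption the range is wider.

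**3. The missing-data rule.** Section 9.5 ignores missing data up to 5%, if missing completely at random. One blank in 30 is 1/30 = 3.3%; two are 2/30 = 6.7%. If blanks are missing data, two already pass the limit. If they mean that all was well, nothing is missing. The plan does not say which.

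**4. Effect on ranking.** Let p be the share of people affected by an aspect and m the share of those who write it down. Expected mentions are 30 × p × m. For two aspects with assumed p of 30% and 20%, the expected order reverses once m for the second exceeds m for the first by more than 30/20 = 1.5 times. The documents give no value of m, so no size can be put on this.

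**5. What a closed item gives at n = 30.** The denominator is the number who answer. The exact (Clopper-Pearson) 95% interval is 2.1% to 26.5% for 3/30, and the upper limit for 0/30 is 11.6%. With complete capture and independent counts, 200,000 simulated studies put the 30% aspect ahead of the 20% aspect in 77%, level in 8% and behind in 15%.

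**The case against.** The strongest reply is that the plan asks for less than this point supposes. Section 9.1 speaks of informing and prioritising risk reduction, not of estimating incidence. Risk scores already exist (section 5.2), within an ISO 14971 process (section 7.3). Written concerns can be coded, counted and set against those scores. The prompts name every aspect, so they are cued questions. All of this stands, and it is why ranking is weakened rather than ruled out.

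The clinician form also has the image item, and its introduction leaves room for items not listed. That stands too, so what the clinician form lacks is known only as far as section 6.4.4 describes it. The image item itself says nothing about set-up or cleaning, and the participant form is not introduced in that open way.

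Other channels exist: session observations (6.2.2), withdrawal reasons (6.5), device deficiencies (8.1.1), adverse event reports (8.2) and the Risk Log update (16). These help with marked problems. However, no recording form is described for the observations, section 6.6 does not list them among the data for which the CRF is the source, and an observer cannot record how hot or heavy the headgear felt.

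It can also be said that closed items at n = 30 will not separate aspects reliably: the exact interval for 3/30 overlaps heavily with that for 6/30 (about 8% to 39%). That is correct. The gain is a known denominator and a severity grade, not precision. Finally, closed items placed before the comments could steer respondents away from unforeseen hazards. This is a fair point, and the fix below puts them afterwards.

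**Conclusion.** The point holds as a worthwhile improvement to the secondary outcomes. As described, the forms give no per-aspect rating and no explicit nil response. Risk prioritisation and score validation would therefore rest on what people choose to write, with frequency and severity unknown for each aspect. The 10%, 15% or up to 43% spread rests on assumed counts and shows the ambiguity; it does not predict its size. The primary endpoint and its test are untouched.

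Four stronger readings are not supported.

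- A reader might infer that the risks cannot be ranked at all. Coded comments and existing scores still allow a ranking, only a less reliable one.
- A reader might infer that the sponsor will treat silence as absence and enter frequencies that are too low. No section says so; the plan simply has no rule for blanks.
- A reader might want a figure for under-reporting. It would depend on the share of affected people who write a comment, which the documents do not give.
- A reader might think that a separate endoscope rating is needed to interpret tolerability. The item asks specifically about the headgear, so such a rating is optional.

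**What to change.** Keep the existing ratings, fractions and comment prompts. Place the free text first, so that unforeseen hazards can be written down before the closed items are answered. After it, add:

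- **Participant form:** one item each for comfort, heat, weight, security and effect on performance, answered none / slight / moderate / severe.
- **Clinician form:** the existing 1 to 5 ease scale, given separately for set-up, operation and cleaning.

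In section 9.1, report x/n for each item, with x defined in advance and n the number who answered, together with the full rating distribution. Give exact 95% intervals for the participant items. For the clinician items give descriptive counts only: the documents do not say how many clinicians will rate, and repeated ratings by one clinician are not independent. State that these counts, alongside the coded comments, set the priorities in the Risk Log.

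The cost is one revised form, a short addition to section 9.1, one descriptive table and about a minute more per respondent. No extra visits or participants are needed. The limitation to state openly is precision: at n = 30 the intervals remain wide.
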